Using Metricwire App		X	X	X		X			

Table 1b. substudy activities and timeline.

The proposed substudy characterizes 1) normative cycle-related variation in neuroactive steroids and mRNA expression, and 2) group-related differences (i.e., past-month SI vs HC) in trajectories of GABAAR subunit change across the cycle. 60 healthy controls (HC) with no SI will be recruited to gain a completer number of 40 for a two-month long observational substudy, in which five lab visits across one menstrual cycle (timed identically to mirror the observations across one medication phase of the experimental trial) will capture baseline molecular/genetic changes for between-group comparisons. The basic timeline for participation can be seen in table 1b.

The **double-blind crossover experimental design** is identical to that used during the PI's recently-completed trial (K99MH109667; Fig. 6). The TOP (red) panel shows natural perimenstrual hormone withdrawal in the placebo condition; the BOTTOM (black) panel shows prevention of hormone withdrawal in the active E2+P4 stabilization condition. THIS IS NOT A CLINICAL EFFICACY TRIAL, but a RCT design will probe the effect of hormone withdrawal (vs. stabilization) on proximal suicide risk and mediators. Participants will be randomized to condition order A (see Table 1 above; Active E2+P4, washout cycle, then Placebo) or condition order B (Placebo, washout cycle, then Active E2+P4). Investigational Drug Services will manage the double-blind. In each two-week condition, participants will wear a weekly patch (E2 or placebo) and take a daily pill (P4 or placebo). Because this manipulation simply delays natural E2+P4 changes⁹⁶, and given our previous finding of benefit¹², this manipulation is *not expected to pose greater risk than a normal menstrual cycle*.

Timing and Duration. Participants will receive the first seven-day transdermal E2 patch (or placebo patch) and begin daily oral P4 (or oral placebo) at a lab visit scheduled seven days after a positive urine ovulation test (+7 in Fig 6). This coincides with a time in the natural cycle when E2+P4 are already elevated. The weekly patch will be changed at the lab visit on day +14. The goal of this E2+P4 manipulation is to extend and maintain the mid-luteal phase hormone profile beyond the point in the cycle (i.e., around day +10) that would normally be associated with natural hormone withdrawal. Therefore, the active condition effectively prevents perimenstrual E2 and P4 withdrawal.

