Overview of Assessment Protocols. Laboratory visits (90 minutes; 7-11 am). After a positive home urine ovulation test (day 0), five 90-minute lab visits will be scheduled on days +7, +10, +14, +18, and +22 across each condition to capture the dynamic changes in mediators and outcomes across the perimenstrual window (Figure 6). Consistent with standard practices in the field of reproductive mood disorders⁵⁵, participants will complete brief (3 minute) daily evening surveys across the study. During the study participants will undergo passive tracking of physiological arousal, movement, and typing speed instability via the Oura Ring, Metricwire App, and BiAffect App, respectively. **Participant Safety Monitoring.** On medication days and 4 days following, daily phone calls (30-60 seconds) will evaluate physical adverse effects and suicide risk.

Enrollment Laboratory Visit (5 hours; split into 2 visits)

Participants will be asked to attend for a 5 hour enrollment session that is split into 2 visits either in-person or virtually in which participants will be learn more about the purpose of the study and will be assessed for eligibility.

Baseline Interviews: The Structured Clinical Interview for DSM-5 (SCID-5)⁹⁷ and Structured Clinical Interview for DSM-5 Personality Disorders⁹⁷, as well as a medical eligibility interview. Lifetime suicidal thoughts and behaviors will be assessed using the Self-Injurious Thoughts and Behaviors Interview -Revised (SITBI-R) and categorized with the C-CASA⁹⁸. Participants will complete the Stress and Adversity Interview (STRAIN)¹⁸ interview, which captures lifetime exposure to adverse events (e.g., Negative Valence Systems of Loss, Threat).

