10.0 Data Analysis and Statistical Considerations

ANALYTIC STEPS

For each outcome, we will use model fit indices to select the best-fitting hierarchical model before proceeding with analyses. Based on our prior study (K99MH109667) with a similar experimental design and similar data collection structure for daily surveys and lab visits, we expect that the data structure for primary analyses will be observations nested within participants (two-level regression model). In our prior models, inclusion of a third level of nesting (i.e., observations nested within condition nested within individuals) did not improve model fit and did not substantively alter hypothesis tests. Based on the prior study, we also expect that a combination of a random intercept for participant and an autoregressive (day-1) within-person error structure will be included based on model fit.

Testing Experimental Effects: Aim 1 and 2 require that we first evaluate the impact of the experiment on each of the 3 primary suicide outcomes and 9 (RDoC, neurosteroid) mediators described above. Therefore, we will first examine effects of the within-person hormone stabilization experiment on repeated measures outcomes across the menstrual cycle.

1. **For daily outcomes**, we will utilize multilevel models (with 52 days—26 per condition--nested within each individual; two-level models) to predict each repeated measures outcome from covariates (daily pain, illness, PRN medication use) and the interaction between (1) **experimental condition** (a dichotomous variable coded as 0 for natural hormone withdrawal condition and 1 for hormone stabilization condition) and (2) **condition phase**, a categorical (contrast) variable coded as follows: *midluteal baseline phase*, coded as days +1 to +7 after the positive ovulation test, *perimenstrual experimental phase*, coded as days +11 to +17 after the positive ovulation test, and the *medication withdrawal phase*, coded as days +22 to +26 after positive ovulation test (see Figure 6 in grant for study design and timeline). **Number of daily observations per person.** For the primary contrast between the midluteal and perimenstrual experimental phases, there are 28 observations per person—14 per condition (7 midluteal, 7 perimenstrual). Based on our preliminary data from the K99 trial (identical experimental manipulation), we anticipate receiving an average of 24 observations per participant.

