Statistical Analysis Plan

Project Title: Cyclical Neuroactive Steroid Changes, Arousal, and Proximal Suicide Risk: An Experimental Approach

Principal Investigator: [name]

Approved as of September 24, 2019

Statistical Analysis Plan

There are twelve total outcomes, which are specified and numbered (#) below. In order to better set up the power analysis details that follow, I have noted the anticipated intra-class correlations for each outcome (in red) and note from which preliminary data these estimates arise.

OUTCOME SPECIFICATION

- Suicide Outcome Variables. In our primary analyses, proximal suicide risk will be operationalized as (1) daily severity of suicidal ideation using the total score on the Adult Suicidal Ideation Questionnaire in the daily survey (ICC=.64 in K99 trial), (2) daily suicidal planning thoughts (dichotomous) on the daily C-SSRS phone risk screen (~10% of days were positive for planning in the K99 trial; ICC=.45 in K99 trial) and (3) daily suicide attempt (dichotomous; aborted, interrupted, or full) on the daily C-SSRS phone risk screen (~1.2% of days were positive for suicide attempt in the K99 trial; ICC=.12 in K99 trial).

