For each outcome, we will use model fit indices to select the best-fitting hierarchical model before proceeding with analyses. Based on our prior study (K99MH109667) with an similar experimental design and similar data collection structure for daily surveys and lab visits, we expect that the data structure for primary analyses will be observations nested within participants (two-level regression model). In our prior models, inclusion of a third level of nesting (i.e., observations nested within condition nested within individuals) did not improve model fit and did not substantively alter hypothesis tests. Based on the prior study, we also expect that a combination of a random intercept for participant and an autoregressive (day-1) within-person error structure will be included based on model fit.

Testing Experimental Effects: Both of our two aims require that we first evaluate the impact of the experiment on each of the 3 primary suicide outcomes and 9 (RDoC, neurosteroid) mediators described above. Therefore, we will first examine effects of the within-person hormone stabilization experiment on repeated measures outcomes across the menstrual cycle.

- a. For daily outcomes, we will utilize multilevel models (with 52 days—26 per condition-nested within each individual; two-level models) to predict each repeated measures outcome from covariates (daily pain, illness, PRN medication use) and the interaction between (1) experimental condition (a dichotomous variable coded as 0 for natural hormone withdrawal condition and 1 for hormone stabilization condition) and (2) condition phase, a categorical (contrast) variable coded as follows: *midluteal baseline phase*, coded as days +1 to +7 after the positive ovulation test, *perimenstrual experimental phase*, coded as days +11 to +17 after the positive ovulation test, and the *medication withdrawal phase*, coded as days +22 to +26 after positive ovulation test (see Figure 6 in grant for study design and timeline). Number of daily observations per person. For the primary contrast between the midluteal and perimenstrual experimental phases, there are 28 observations per person—14 per condition (7 midluteal, 7 perimenstrual). Based on our preliminary data from the K99 trial (identical experimental manipulation), we anticipate receiving an average of 24 observations per participant.

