- Power in multi-level models has a unique consideration beyond sample size and alpha; it is dependent also on the intraclass correlation (ICC) and its implications for the independence of level-1 observations (i.e., the design effect). High ICCs indicate little variation of the outcome within a given person (i.e., stability of repeated observations within a given person), and suggest that the study's power depends more on the number of higher-level units. Low ICCs indicate high within-person variation within a given person and suggest that the study's power depends more on the number of lower-level units. As the ICC ranges from 0 to 1, the effective n will range from the number of lower-level units to the number of higher-level units. In general, the lower the ICC, the higher the power.
- Snijders and Bosker (1999; *Multilevel Analysis: An Introduction to Basic and Advanced Multilevel Modeling*) provide equations to determine the "Design Effect", which we have used to calculate the "effective lower-level N" based on our expected ICCs for each outcome and our expected number of raw observations with 85 completer participants (including 15% missing at daily level and an average of .25 missing visits per person). Once the design effect and effective N is calculated for a given outcome, one can calculate power to detect a given effect size (in our case, f² = .10) for a given number of these *effective* lower-level units (observations or visits)— see Table below for estimates for the current design. We considered a single fixed regression coefficient in a model with 3 predictors, one-tailed test, alpha=.004.
 

Variable	Measureme nt interval	ICC	Upper-Level Sample Size	Effective Lower- Level N based on ICC and Design Effect Equation	Power Achieved to detect f ² = .10
Suicidal Ideation	Daily	.64	85	130	.81
Suicidal Planning	Daily	.45	85	180	.93
Suicide Attempt	Daily	.12	85	542	.99
Beck Hopelessness Scale	Daily	.32	85	244	.98
Brief Agitation Measure	Daily	.26	85	292	.99
Accelerometer activity	Daily	.54	85	152	.88
Typing Speed Instability	Daily	.38	85	209	.96
HRV withdrawal in the lab	Labs	.50	85	163	.90
PEP shortening in the lab	Labs	.50	85	134	.83
Allopregnanolone in serum	Labs	.29	85	177	.93
PBMC gene expression for 3a- HSD	Labs	.50	85	134	.83
PBMC gene expression for 5a- reductase	Labs	.50	85	134	.83

1 R01 MH120843-01 (PI: [name])

Additional Requested Supplemental Table (2019-08-16)

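### Planning and attempt (primary outcomes 2 and 3) come from phone calls that reach only 1 of the 7 baseline days their condition-by-phase test counts

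*Protocol*

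**What the plan says.** **Source of the outcomes.** SAP, Outcome Specification. Outcome 2 is daily planning, "dichotomous) on the daily C-SSRS phone risk screen (~10% of days were positive for planning in the K99 trial". Outcome 3 is daily attempt, "dichotomous; aborted, interrupted, or full) on the daily C-SSRS phone risk screen".

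**Test.** SAP Analytic Steps (a) and protocol section 10.0 apply one model to all daily outcomes: condition by phase. Baseline is "coded as days +1 to +7 after the positive ovulation test", the perimenstrual phase is days +11 to +17 and the withdrawal phase is days +22 to +26. For the main contrast, "there are 28 observations per person—14 per condition (7 midluteal, 7 perimenstrual"; about 24 are expected to arrive.

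**Power.** The SAP table uses "our expected number of raw observations with 85 completer participants (including 15% missing at daily level" and credits planning with effective N 180 and power .93, and attempt with 542 and .99.

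**Call schedule.** Protocol section 6.0, Participant Safety Monitoring: "On medication days and 4 days following, daily phone calls (30-60 seconds) will evaluate physical adverse effects and suicide risk". Under Timing and Duration, participants "begin daily oral P4 (or oral placebo) at a lab visit scheduled seven days after a positive urine ovulation test", and each condition lasts two weeks.

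**Other mentions of calls.** Table 1a, as far as its broken layout can be read, marks calls once per study phase and evening surveys throughout, which agrees. Section 7.0 places calls within each condition. The Daily Symptoms Survey paragraph in section 6.0 covers all four months and refers to a safety call the next day, without saying on which days calls are made.

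**The concern.** The instrument for two of the three primary suicide outcomes is not scheduled on six of the seven days that form their baseline. The seventh, day +7, is called only after the first patch has been applied, and the order of that call and the evening pill is not stated. So there is no untreated daily phone baseline.

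The model can still be fitted, but the baseline side of the interaction would rest on one post-patch day per condition. Unless this is settled beforehand, someone must choose a baseline once data exist: the single day, a recall interview at the laboratory visit, or none. The choice also feeds the mediation analysis, which goes ahead for a suicide outcome only if the experimental effect on that outcome is significant.

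**Working it through.** **1. Days covered.** Fourteen daily pills from day +7 end on day +20; the second weekly patch, applied on day +14, ends on day +21. Adding 4 days, calls run from +7 to +24 or +25.

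| Phase | Days | Called |
|---|---|---|
| Baseline | +1 to +7 | 1 of 7 |
| Perimenstrual | +11 to +17 | 7 of 7 |
| Withdrawal | +22 to +26 | 3 or 4 of 5 |

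Contrast observations per person: 2 × (1 + 7) = 16, against 2 × (7 + 7) = 28. After 15% missing: 13.6 against 23.8 (the SAP rounds to 24).

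**2. The SAP's figures.** Effective N = n·m / (1 + (m − 1)·ICC), with n = 85. Power for one coefficient comes from the noncentral t, with df = N − 4, noncentrality √(f²·N), f² = .10 and one-tailed alpha .004.

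- Planning, ICC .45, m = 24: 2040 / 11.35 = 179.7, power .939 (stated 180, .93).
- Attempt, ICC .12, m = 24: 2040 / 3.76 = 542.6, power above .99 (stated 542, .99).

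The table therefore does credit the phone outcomes with the full 28-day schedule.

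**3. Same formula on the called days, m = 13.6.**

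- Planning: 1156 / 6.67 = 173.3, power .93.
- Attempt: 1156 / 2.512 = 460.2, power above .99.

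Losing six of seven baseline days barely registers, because the formula counts observations without regard to the side of the contrast on which they fall.

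**4. Variance of the contrast itself.** Take mean(+11 to +17) minus mean(baseline) within a condition, with AR(1) errors; both documents expect an autoregressive structure. The rho values are assumed, and this is a linear approximation for a binary outcome.

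| rho | Variance, day +7 only / days +1 to +7 | 85 people equal, on the planned schedule |
|---|---|---|
| 0 | 4.00 | 21 |
| .2 | 2.98 | 28 |
| .4 | 2.23 | 38 |
| .6 | 1.64 | 52 |
| .8 | 1.15 | 74 |

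**5. Baseline information for planning.** Baseline person-days fall from 85 × 2 × 7 × .85 = 1,011.5 to 85 × 2 × 1 × .85 = 144.5, sevenfold.

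- If the SAP's 10% rate held on baseline days: about 101 positive days become 14.5.
- If 10% is the average over equal numbers of baseline and perimenstrual days, and the odds ratio of 4.29 in protocol section 2.0 applies: the rates are about 4.2% and 15.8%, since (.158/.842) / (.042/.958) ≈ 4.29. About 42 positive days become 6.

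Both counts are illustrative; the sevenfold ratio is not.

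**6. Comparing conditions on days +11 to +17 only.** Without person-by-cycle variance, the variance is .50 to .63 of the planned contrast (rho 0 to .8). It stays at or below the planned variance while person-by-cycle variance is under .14 to .39 of the daily within-person variance (break-even = planned contrast variance minus the variance of the 7-day mean).

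**The case against.** **The calls may be more frequent than section 6.0 says.** The survey paragraph can be read as implying a call after every survey day. It gives no dates, whereas the monitoring sentence does and Table 1a appears to agree. This is a conflict to reconcile; it does not establish calls on days +1 to +6.

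**A reader might infer that the stated power collapses.** The documents do not support that. By the SAP's method, planning power moves from .94 to .93 and attempt power stays above .99. The loss lies in a feature the method cannot see, and its size depends on a rho the documents do not give. At .8 it is modest.

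**A reader might also infer that the aim cannot be tested for these outcomes.** That is wrong too. Aim 1a predicts higher risk under perimenstrual withdrawal than under perimenstrual stabilization. This is a comparison of randomized conditions in a window that is fully called. What fails is the SAP's change-from-baseline form of it.

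**The day +7 laboratory visit offers a baseline.** In part. It includes the ASIQ and a C-SSRS interview, listed before patch application, but these are not daily and are not the source the SAP names. The C-SSRS looks back to the previous visit. In phase 2 that is phase 1 day +22, two cycles minus 15 days earlier: 27 to 55 days for the eligible 21- to 35-day cycles.

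**Planning may already be asked every evening.** The SAP places the ASIQ total in the daily survey, and the protocol says the ASIQ has planning items. This objection stands and shapes option (b) below. However, the protocol's list of evening-survey content omits the ASIQ.

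**Conclusion.** The point holds as a mismatch between outcome source, call schedule and baseline window. Outcomes 2 and 3 have 1 of 7 baseline days, so 16 scheduled contrast observations per person and not 28, and the stated effective N counts days without calls.

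The consequence is a weaker baseline contrast, with about 1.2 to 4 times the planned variance for assumed rho of .8 to 0, and a sevenfold drop in baseline planning data. No power figure is offered for either outcome under the actual schedule: the documents give neither rho nor an effect size on the binary scale, and the linear approximation is weak for attempts at about 1.2% of days.

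Outcome 1 is not touched by the call schedule, though whether the ASIQ is in the evening survey bears on it. The plan should be corrected before analysis.

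**What to change.** Reconcile protocol section 6.0 (call days and evening-survey content) and section 10.0 with the SAP's Outcome Specification, Analytic Steps and Power Analysis. Leave the safety calls as they are. If calls are in fact made on days +1 to +6, correcting the monitoring sentence resolves the schedule conflict. Otherwise:

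**(a) Outcomes 2 and 3.** Define the primary test as active against placebo on days +11 to +17, with period in the model. Align the hypothesized pattern, the mediation gate and the indirect effect with that contrast for these two outcomes. Restate 14 scheduled observations per person (14 × .85 = 11.9 expected), and replace the tabulated power with a simulation of the actual model on those days, labelled illustrative where effects are assumed.

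Cost: wording and a simulation; no new data, calls or visits. Downside: no within-cycle baseline adjustment, so cycle-to-cycle shifts enter the error. The report from the earlier trial that "inclusion of a third level of nesting (i.e., observations nested within condition nested within individuals) did not improve model fit" suggests these are small, but that crossover had 30 participants.

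**(b) Outcome 2 only, if the ASIQ is in the evening survey.** Define planning from its planning items, with baseline days +1 to +6. Scheduled observations are 2 × (6 + 7) = 26 (22.1 expected), and contrast variance is 1.07 to 1.08 times that of a seven-day baseline. This keeps the change-from-baseline test at little added cost, and the protocol's earlier planning results also used the ASIQ. Downside: it departs from the phone instrument behind the SAP's 10% rate and ICC of .45, and outcome 3 still needs (a).

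In either case, name the call item that defines the outcome: the SAP says C-SSRS, while protocol section 7.0 says the calls end with the UWRAP.
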